9 10 11	STA 8.1 8.2 8.3 SA 9.1 9.2 10.1 10.2 10.3 10.4 11.1	ATISTICAL PLAN SAMPLE SIZE DETERMINATION STATISTICAL METHODS SUBJECT POPULATION(S) FOR ANALYSIS FETY AND ADVERSE EVENTS RECORDING OF ADVERSE EVENTS WHEN ADVERSE EVENTS ARE RECORDED DATA HANDLING AND RECORD KEEPING CONFIDENTIALITY SOURCE DOCUMENTS CASE REPORT FORMS RECORDS RETENTION STUDY MONITORING, AUDITING, AND INSPECTING STUDY MONITORING PLAN ETHICAL CONSIDERATIONS STUDY FINANCES	10111111121212131313141414	
9 10 11	STA 8.1 8.2 8.3 SA 9.1 9.2 10.1 10.2 10.3 10.4 11.1	ATISTICAL PLAN SAMPLE SIZE DETERMINATION STATISTICAL METHODS SUBJECT POPULATION(S) FOR ANALYSIS FETY AND ADVERSE EVENTS RECORDING OF ADVERSE EVENTS WHEN ADVERSE EVENTS ARE RECORDED DATA HANDLING AND RECORD KEEPING CONFIDENTIALITY SOURCE DOCUMENTS CASE REPORT FORMS RECORDS RETENTION STUDY MONITORING, AUDITING, AND INSPECTING STUDY MONITORING PLAN ETHICAL CONSIDERATIONS STUDY FINANCES FUNDING SOURCE	101111111212	
9 10 11	8.1 8.2 8.3 SA 9.1 9.2 10.1 10.2 10.3 10.4 11.1 13.2 13.3	ATISTICAL PLAN SAMPLE SIZE DETERMINATION	101011	
9 10 11 12 13	STA 8.1 8.2 8.3 SA 9.1 9.2 10.1 10.2 10.3 10.4 11.1 13.1 13.2 13.3	ATISTICAL PLAN SAMPLE SIZE DETERMINATION STATISTICAL METHODS SUBJECT POPULATION(S) FOR ANALYSIS IFETY AND ADVERSE EVENTS RECORDING OF ADVERSE EVENTS WHEN ADVERSE EVENTS ARE RECORDED DATA HANDLING AND RECORD KEEPING CONFIDENTIALITY SOURCE DOCUMENTS CASE REPORT FORMS RECORDS RETENTION STUDY MONITORING, AUDITING, AND INSPECTING STUDY MONITORING PLAN ETHICAL CONSIDERATIONS STUDY FINANCES. FUNDING SOURCE INDEMNITY FOR THE PERFORMANCE OF THE STUDY SPONSORSHIP	10	

Study Summary

Title	Defining the long term consequences of acute kidney injury: the AKI Risk In Derby (ARID) study
Short Title	AKI Risk In Derby (ARID) study
Protocol Version Number and Date	Version 1.4 December 2015
Methodology	Long term case-control study.
Study Duration	Twelve years and nine months. See section 3.1 for details.
Study Centres	Royal Derby Hospital
Objectives	To assess the effect of Acute Kidney Injury (AKI) on long term patient outcomes, specifically looking at the effect on progression of chronic kidney disease (CKD) and mortality rates. To identify clinical and biochemical markers that predict those at greatest risk of CKD progression
Number of Subjects/Patients	1084
Main Inclusion Criteria	Identified as AKI or Not AKI (NAKI) on iCM electronic reporting system Age ≥18 years and ≤85yrs Able to provide full informed consent
Statistical Methodology and Analysis	Descriptive statistics to summarise baseline variables. Kaplan-Meier curves to compare the primary endpoints. A Cox proportional hazard model to test the effect of AKI on primary endpoints adjusted for important co-factors.

1. Introduction

The described research study will be conducted in compliance with the protocol, the Research Governance Framework, International Conference on Harmonisation, Good Clinical Practice Guideline ICH/GCP, and all applicable Derby Hospitals NHS Foundation Trust Research Office requirements.

1.1 Background

Acute Kidney Injury (AKI) is very common in acutely ill patients and is associated with longer, more complicated hospital stays and worse patient survival. The RIFLE criteria and subsequent modification by AKIN now provide a widely accepted definition of AKI that is predictive of short term outcomes [1]. Mortality progressively increases with severity of AKI; the mortality rate of critically ill patients on the intensive care unit (ICU) who receive renal replacement therapy (RRT) ranges between 50-80% [1]. There is now an increasing recognition that episodes of AKI may also have profound longer term sequelae. There are some studies suggesting that AKI leads to chronic kidney disease (CKD) and increases the risk of end-stage renal failure requiring dialysis [2-7]. Clearly this is very important as CKD and dialysis in particular have major effects on patient well-being and symptomatology; it follows that survivors of AKI may also have a worse long term survival rate as compared to those who do not sustain AKI [3, 8, 9]. There are also huge health economic implications bearing in mind the annual cost of haemodialysis for just one patient is £30,000.

However, the majority of studies in this area are retrospective and many include only specific patient groups such as ICU patients who required RRT, those undergoing surgical procedures or following coronary angioplasty. Furthermore, several of the published studies are historical and do not use the current diagnostic criteria for AKI [2, 4, 10, 11]. It is therefore unclear as to whether an association really exists between AKI and long term outcomes in a general hospitalised population who form the largest group of patients sustaining AKI. In addition, it remains to be seen whether associations between AKI and outcomes are causal, and whether patients at higher risk of subsequent adverse outcomes can be identified to allow targeting of follow up and more intensive management to those with the greatest clinical need. This will also inform the design of future interventional research studies.

The progression of CKD is determined by several factors but progressive tubular damage and inflammation both lead to fibrosis [12]. Tubular injury and inflammation are also key in the development and propagation of AKI; biomarkers of tubular damage such as neutrophil gelatinase-associated lipocalin (NGAL) and circulating markers of inflammation such as interleukin-6 (IL-6) both correlate with the onset and severity of AKI [13, 14]. Although there are initial data suggesting NGAL can predict progression of

CKD [15], these data are limited and it is uncertain how these factors interact to affect CKD progression that follows episodes of AKI.

There is therefore a need to examine the long term effects of AKI on patient outcomes in a prospective, UK based study that includes patients across the entire severity spectrum of AKI and across a broad range of clinical scenarios and specialities.

2 Study Objectives

The objectives of the study are to determine the long term effects of AKI on progression of CKD and mortality rates by comparing outcomes in hospitalised patients with similar characteristics who did and did not sustain AKI.

We also seek to define profiles of patients (using clinical parameters, biomarker profiles or a combination of both) that allow identification of those at highest risk of CKD progression.

3 Study Design

3.1 General Design

This is a long-term longitudinal observational case-control study. Basic blood tests to include measuring renal function, haemoglobin, albumin and proteinuria will be measured at study entry as well as 1 year, 3 years, 5 years and 10 years after AKI (approximately 9months, 33months, 57 months and 117 months after recruitment). Samples will also be collected and stored at each of these time points for subsequent biomarker measurement; these will consist of inflammatory markers (IL-6, high sensitivity CRP) and plus a panel of biomarkers of tubular injury (to include NGAL and IL-18). Included patients will have baseline demographics, co-morbidity and acute illness details extracted from the hospital PAS system. AKI stage and baseline renal function (that prior to sustaining AKI) will be extracted from the electronic AKI reporting system currently in clinical use at the Royal Derby Hospital. This novel system identifies all episodes of AKI from every inpatient location and also reports severity as per AKIN staging; the diagnostic accuracy of this system has been confirmed and reported previously [16].

Patients receiving acute dialysis during the episode of AKI will be identified from renal unit and intensive care unit databases; the renal database (Vitaldata) will be used to identify those patients who subsequently require chronic renal replacement therapy (RRT). The Medical Research Information

Service (MRIS, an arm of the NHS Information Centre) will be used to accurately track survival data of participants to **ten** years after the AKI episode.

A pilot study, specifically designed to test this methodology and recruitment process is currently underway, and demonstrates that the proposed recruitment, consent and matching processes are both practicable and feasible (recruitment rate ~20%, with approximately 15 participants recruited per week).

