3.2 Primary Study Endpoints

- 1. The risk of death in AKI group versus controls.
- 2. The risk of CKD progression in AKI group versus controls.

CKD progression will be defined as doubling of serum creatinine, eGFR<15mls/min or the initiation of renal replacement therapy (dialysis or transplantation).

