3.3 Secondary Study Endpoints

- 1. Proportion of patients reaching renal endpoint (doubling creatinine/ESRF)
- 2. Mortality rates at each time point.
- 3. Length of hospital stay.
- 4. Estimated glomerular filtration rate (eGFR), serum creatinine and urine protein:creatinine ratio at each time point.
- 5. Comparison of causes of death between AKI group and controls
- 6. Comparison of levels of biomarkers of tubular injury (a panel to include NGAL and IL-18) and markers of inflammation (IL-6, hs-CRP) in those with and without progression of CKD.

4 Methods

The methods are the same as for the pilot study; the only change is that we propose to collect an additional blood sample for storage and subsequent analysis at each time point.

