4.2 Subject Recruitment and Screening

There will be two methods of patient recruitment. For the majority of patients, the recruitment will occur as in the pilot study and is detailed in section 4.2.1. For a specific group of patients with liver disease, we propose a modified method of recruitment to adapt to the challenges of participant engagement in this particular patient group; this is detailed in section 4.2.3.

All patients will be identified via the AKI electronic reporting system. This system will electronically identify all patients that have sustained AKI or been screened for possible AKI but who did not sustain it. This database is currently used internally to monitor trends and assess effectiveness of clinical care. We will apply for specific ethical approval from the National Information Governance Board (approval for the same methodology already in place for the pilot study) to allow the identification of potential participants from this database, even though their inpatient care may have been delivered by another clinical team.

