4.2.1 Group A – main study

All patients with AKI will be screened for inclusion into the study, as well as those patients tested for possible AKI but who did not sustain it. Patients will not be approached until at least two months after they have recovered from their acute illness, by which time the majority of patients will have returned home.

Recruitment, matching and consent

Patients who meet the inclusion criteria will be contacted via post and invited to participate. The control group will be matched to AKI patients on a 1:1 basis in terms of baseline eGFR (within the same CKD stage but as closely as possible) and age \pm 5yrs. In addition they will be recruited from a similar inpatient setting. Due to the proposed three year follow up, patients over 85yrs will be excluded as the reduced life expectancy due to age alone in these patients may affect the outcome measures of mortality.

Potential subjects will receive a letter of invitation along with a comprehensive patient information sheet. Interested patients will be asked to telephone a number at the Royal Derby Hospital during which patient identity will be affirmed using standard data protection questions. After confirmation that the patients are in possession of the information required to provide valid consent, they will be sent a consent form that they will sign and return in a pre-paid envelope, retaining a copy for themselves (see section 4.2.2 for more details of the consent process). If patients do not wish to participate they will be asked to confirm this by telephoning the same number. This methodology has been piloted and has been shown to be very successful in more than 300 patients to date, with very positive feedback from participants.

Each patient will be assigned a unique study number that will be used to identify all data collected for the study. This will be allocated upon recruitment. A key of patient identity and study numbers will be kept on a password-protected Trust server in a password-protected file. Any information passed onto the Medical Research Information Service will be in encrypted form. A recruitment log will be maintained and the patients' GPs will be informed of their participation in the study by letter.

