8.1 Sample Size Determination

The original sample size for the study was based on some assumptions and information published in two studies [10, 11] so in line with the statistical plan in version 1.2 of the protocol, the sample size calculation has been repeated using one year results from the pilot study. The new sample size calculation is based on percentage change in eGFR at one year, a surrogate for subsequent CKD progression (doubling of serum creatinine or progression to CKD stage 5/dialysis). A previous study reported that 21.4% of those who experienced a 20% fall in eGFR at one year progressed to initiation of RRT [18]. Results from the pilot study have shown that 13 patients experienced such a decline in eGFR at one year in the control group as compared to 29 in the AKI group. Therefore, the estimated proportion in the control group that will progress to a doubling of serum creatinine or progression to CKD stage 5 is 2.02% as compared to 4.41% of the AKI group. Assuming a 5% significance level and 80% power this means that 430 patients will be required per group. Assuming a drop-out rate of 26% then a total of 542 patients will be required in each group.

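### The system that flags AKI also supplies the baseline used for matching, so regression to the mean can make AKI patients' follow-up eGFR look lower than their matched controls' when AKI has no effect

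*Protocol*

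**What the plan says.** All references are to the protocol.

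- **Group assignment (4.2).** "This system will electronically identify all patients that have sustained AKI or been screened for possible AKI but who did not sustain it".
- **Baseline (3.1).** "AKI stage and baseline renal function (that prior to sustaining AKI) will be extracted from the electronic AKI reporting system". This is the only place that says what baseline renal function means. It does not say how many creatinines form the value or how the system derives it.
- **Matching (4.2.1, repeated for the liver group in 4.2.3).** "The control group will be matched to AKI patients on a 1:1 basis in terms of baseline eGFR", within the same CKD stage and as closely as possible, plus age within 5 years.
- **Adjustment (8.2).** The Cox model includes baseline renal function, with no other definition offered.
- **Endpoints (3.2, 3.3).** One primary endpoint is death. The other is renal: "CKD progression will be defined as doubling of serum creatinine, eGFR<15mls/min or the initiation of renal replacement therapy (dialysis or transplantation"). No reference creatinine is named for doubling. A secondary endpoint is "Estimated glomerular filtration rate (eGFR), serum creatinine and urine protein:creatinine ratio at each time point".
- **Sample size (8.1).** It is built on percentage change in eGFR at one year, again with no reference named: "13 patients experienced such a decline in eGFR at one year in the control group as compared to 29 in the AKI group".
- **A second possible reference (3.1, 5).** Renal function is also measured at recruitment, about three months after the episode.

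**The concern.** A measured creatinine is the patient's usual level plus day-to-day and assay variation. If AKI is declared when the inpatient value is high relative to baseline, a patient whose baseline was low by chance is more likely to be flagged, and one whose baseline was high by chance is more likely to become a control. Matching on measured baseline then pairs an AKI patient whose true eGFR is lower than measured with a control whose true eGFR is, if anything, higher. At follow-up both return towards their true levels and the AKI patient looks worse. Adjusting for the same value compares the same mismatched patients, so it does not help.

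The study sets out to compare patients with similar characteristics and asks whether the association is causal. A mismatch in true starting eGFR that leans towards an AKI effect goes to that aim, most directly for eGFR and creatinine at each visit.

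**Working it through.** **1. The pilot figures in 8.1.** The projected event rates are 2.02% and 4.41%, and 21.4% of those with a 20% eGFR fall are taken to progress. The implied one-year 20%-fall rates are:
- controls: 2.02/21.4 = 9.4%
- AKI: 4.41/21.4 = 20.6%
- gap: 20.6 - 9.4 = 11.2 points

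With 13 and 29 patients these rates imply about 138 controls and 141 AKI patients.

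**2. Model with no AKI effect.** The protocol gives none of these inputs, so all are assumptions. True log-creatinine is stable (SD 0.35 across patients). Baseline, peak and follow-up each carry an independent error of SD s. A fraction of 20-30% of patients have an exponential acute log-rise with mean 0.3-0.6. AKI is flagged if peak/baseline >= 1.5. eGFR is proportional to creatinine^-1.2. Controls are reweighted to the AKI group's measured baseline, which mimics close matching.

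**3. Spurious deficit in follow-up eGFR, AKI against matched controls, single-value baseline.**

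| Within-person SD | Deficit (%) |
|---|---|
| 5% | 0.6-1.0 |
| 8% | 1.5-2.7 |
| 10% | 2.5-4.5 |
| 12% | 4.0-7.2 |

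With a baseline that averages three values, the deficit is 0.2-2.3% over the same SDs (0.8-1.4% at SD 10%).

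**4. Sensitivity to the assumed acute rise.** Replacing the exponential rise by a normal one truncated at zero (exponent 1.154) gives larger gaps with a single value: 1.3-4.6 points at SD 5% and 4.7-12.2 at SD 10%. The direction is the same; the size depends on inputs that the protocol does not supply.

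**5. Which reference is used for change.**
- *System baseline as reference, exponential rise.* The excess of 20% falls, as a share of the 11.2-point pilot gap, is:
  - SD 5%: 0.1-0.2 points, or 1-2%.
  - SD 8%: 1.3-2.6 points, or 12-23%.
  - SD 10%: 12.4-14.9% against 9.4%, so 3.0-5.5 points, or 27-49%.
  - SD 10% with a mean of three: 0.6-1.3 points, or 5-12%.
- *System baseline as reference, truncated-normal rise.* The middle setting at SD 10% gives 16.0% against 7.9%, so 8.1 points, or 72%.
- *Three-month sample as reference.* The change artefact vanishes (SD 10%: +1.3% in both groups, 20% falls 8.6% in both). The difference in follow-up level does not, because it comes from the matching: 2.5-4.6% at SD 10% with the exponential rise.

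**6. Primary endpoint.** Spurious creatinine doubling stays below 0.01% at SD 10%. At SD 15% it is 0.1-0.4% in AKI against 0.02-0.04% in controls.

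**7. Does an independent earlier value repair it?** As the reference for a change score it brings the difference to zero. As the covariate in place of the system value, the share removed is about its reliability. At SD 10% that is 0.35²/(0.35² + 0.10²) = 0.1225/0.1325 = 0.92, which agrees with about 90% in simulation. If the analysis also conditions on the system value, the remaining true variance is 0.1225 × 0.01/0.1325 = 0.00925, and the share falls to 0.00925/(0.00925 + 0.01) = 0.48.

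**The case against.** The strongest reply is that two links are missing from the document. It nowhere says that the baseline is a single creatinine. It also nowhere says that this baseline is the reference for doubling or eGFR change, a choice often left to the statistical analysis plan, and a three-month sample is available for it. The primary endpoints are essentially untouched: "The risk of death in AKI group versus controls" involves no creatinine reference, nor do eGFR<15 or RRT, and doubling hardly moves. Eight-step assumptions about variability and acute rise drive every magnitude. The proposed remedy needs earlier results that the system did not use, and few may be left if it already pools them.

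Most of this stands, and it limits the point. A reader might infer that one pre-admission creatinine serves as flag, match and outcome baseline; the text supports the flag and the match, but not the number of values or the outcome reference. A reader might also infer that a quarter to a half of the pilot's contrast is artefact. That holds only for a single-value pre-AKI reference at SD 10% with the exponential rise, and the share is nil if change was measured from the three-month sample.

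The reply does not dispose of the matching. Section 3.1 and section 4.2 fix the common source of flag and baseline, averaging shrinks the error without removing it, and a three-month reference leaves the level difference in place. That sample is also taken after the injury, so using it as reference would leave out any early loss due to AKI.

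**Conclusion.** The point holds for the matched comparison. One system assigns AKI status and supplies the matching baseline and, as the only baseline the protocol defines, apparently the Cox covariate. Provided the flag is a rise from that baseline, matched AKI patients start with lower true eGFR than their controls. Under a 1.5-fold flag, SDs of 5-12% and the exponential rise, the spurious follow-up deficit is about 0.6-7% with one value and 0.2-2.3% with a mean of three; other rise distributions can give more.

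What is affected is the secondary comparison of eGFR and creatinine levels, the adjustment for baseline, and possibly the pilot surrogate in 8.1. How much of 13 against 29 is artefact cannot be determined from the protocol. It would be wrong to read this as a demonstrated bias in the primary results: the effect on doubling is negligible, and none has been shown on death, eGFR<15 or RRT. This is a worthwhile, inexpensive improvement and does not invalidate the design.

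**What to change.** In 3.1 and 8.2:

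1. State how the system derives baseline, and name the reference creatinine for doubling and for percentage eGFR change.
2. Keep existing pairs. Where available, take pre-admission creatinine results that the system did not use for flagging (for example the mean of the others in the prior year), by the same rule in both groups. Use this value as the reference for eGFR change and doubling, and as the baseline covariate. As covariate it should replace the system value; conditioning on both, as covariates or through the pairs, recovers only about half of the bias at SD 10%.
3. Fall back on the system value where nothing else exists, with a sensitivity analysis excluding those patients.
4. If the pilot's 20% falls were counted from the system baseline, recount them on this reference.

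The cost is a pull of earlier results from the hospital results system, which are not among the data items now listed, and a few sentences. The downside is that some patients will have no other earlier result, and availability may differ between groups, so it should be reported by group.

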3.2 Primary Study Endpoints

- 1. The risk of death in AKI group versus controls.
- 2. The risk of CKD progression in AKI group versus controls.

CKD progression will be defined as doubling of serum creatinine, eGFR<15mls/min or the initiation of renal replacement therapy (dialysis or transplantation).

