4.1 Subject Selection and Withdrawal

4.1.1 Inclusion Criteria

- Age ≥18 years and ≤85yrs
- In-patient serum creatinine measurement detected by iCM electronic AKI reporting system

Exclusion Criteria

- Inability/refusal to give informed consent to participate.
- Language barrier that prevents informed postal consent.
- Death during the same hospital admission that AKI occurred.
- Receiving palliative care

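### The eGFR<15 component of the renal primary endpoint can be met before the index admission, and its RRT component is not tied to chronic RRT

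*Protocol*

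**What the plan says.** Protocol section 3.2 gives the renal primary endpoint as: "CKD progression will be defined as doubling of serum creatinine, eGFR<15mls/min or the initiation of renal replacement therapy (dialysis or transplantation". The second component is an absolute threshold. The section does not require that the patient was above it before.

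Entry is wide. Besides the age limits, section 4.1.1 asks only for "In-patient serum creatinine measurement detected by iCM electronic AKI reporting system". The four exclusions concern consent, language, palliative care and "Death during the same hospital admission that AKI occurred". None concerns renal function. In sections 4.2.1 and 4.2.3 controls are matched on age and on baseline eGFR, "within the same CKD stage but as closely as possible".

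Sections 4.3 and 8.3 keep all patients in the analyses, with one exception: controls who later sustain AKI.

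On RRT, section 3.1 separates two things. "Patients receiving acute dialysis during the episode of AKI will be identified from renal unit and intensive care unit databases", while the renal database serves to "identify those patients who subsequently require chronic renal replacement therapy (RRT". Section 3.3 names the renal endpoint as doubling of creatinine or end-stage renal failure.

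**The concern.** A threshold counts as progression only if the patient starts on the other side of it. As written, someone with stage 5 disease or on maintenance dialysis before the index admission may enter, may be matched to a control in the same stage, stays in the analysis set, and meets the eGFR<15 component with no change in kidney function. Such patients say nothing about the effect of AKI. If they occur about equally in both groups, which matching within stage makes likely, they bring the two event proportions closer in relative terms. Few renal events are expected, so a handful of prevalent cases matters.

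The RRT component has a separate wording problem. Section 3.2 speaks of any initiation of RRT, section 3.1 of chronic RRT that follows, and section 3.3 of end-stage disease. A primary endpoint should be readable from its own definition.

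**Working it through.** **Eligibility and analysis set**

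1. Does the definition require a new event? For eGFR<15, no (section 3.2).
2. Does eligibility remove prevalent cases? No (section 4.1.1 and the exclusion list).
3. Does matching remove them? No. It only requires the control to be in the same stage (sections 4.2.1 and 4.2.3).
4. Does the analysis set remove them? No. The only exception is controls with later AKI (sections 4.3 and 8.3).

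**RRT wording**

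- Section 3.2: initiation of RRT, unqualified.
- Section 3.1: acute dialysis in the AKI episode is identified from one set of databases, later chronic RRT from the renal database.
- Section 4.4: acute dialysis and dialysis independence are recorded as details of the index episode.
- Section 8.2: the need for acute dialysis is a covariate in the Cox model.

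Three sections treat index dialysis as something other than the outcome. Only section 3.2 is silent.

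**Size**

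Inputs from section 8.1: expected proportions of 2.02% (control) and 4.41% (AKI), and 430 patients per group. These rates are built from a one-year fall in eGFR, so they describe new events.

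The stated 430 does not reproduce from these rates: the usual two-sided formula at 5% and 80% power gives 854 per group, and power at 430 is about 51%. That is a separate matter. Here 430 serves only as the denominator.

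Expected events: 430 × 0.0202 = 8.7 control; 430 × 0.0441 = 19.0 AKI. Risk ratio: 0.0441 / 0.0202 = 2.18.

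Let a share x of both groups be below 15 before the index admission and be scored as events, with everyone else at the plan's rate. The observed proportion is then p′ = x + (1 − x)p. The protocol gives no value for x, so a range is shown. For x = 1%: control 0.01 + 0.99 × 0.0202 = 3.00%; AKI 0.01 + 0.99 × 0.0441 = 5.37%; ratio 1.79.

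| x (assumed) | Prevalent cases per 430 | Control | AKI | Risk ratio | Power at 430 |
|---|---|---|---|---|---|
| 0 | 0 | 2.02% | 4.41% | 2.18 | 51% |
| 0.5% | 2.2 | 2.51% | 4.89% | 1.95 | 46% |
| 1% | 4.3 | 3.00% | 5.37% | 1.79 | 41% |
| 2% | 8.6 | 3.98% | 6.32% | 1.59 | 34% |

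The absolute difference hardly moves (2.39 points at x = 0, 2.34 at x = 2%). The ratio falls and the variance rises. At x = 2% about half of the control events (0.02 / 0.0398) would be prevalent cases.

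**The case against.** Section 3.2 calls the endpoint progression, section 3.3 speaks of patients reaching it, and section 8.1 of progression to stage 5. A sensible analyst would take all three to mean a new event. The risk set and the handling of events at time zero are often left to a statistical analysis plan, which is not shown. The Cox model adjusts for baseline renal function, and in the 12-month conditional logistic regression a pair with both members at the endpoint contributes nothing. The protocol does not show that any stage 5 patient would be enrolled, and does not say whether the electronic system filters out maintenance dialysis patients.

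Part of this stands. The intent is probably a new event, the table is crude and unadjusted, and the number of such patients is unknown. But eligibility and the primary endpoint definition belong in the protocol, and an analysis plan that removed these patients would contradict sections 4.3 and 8.3. The Kaplan-Meier curves and log-rank test are unadjusted. Adjustment for baseline function does not turn a prevalent state into an event.

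Two stronger readings are tempting, and the protocol does not support them. A reader might infer that dialysis for the index AKI itself counts as the outcome, which would inflate the AKI effect. Section 3.2 alone does not exclude this, but sections 3.1, 4.4 and 8.2 show that it is not meant. A reader might also infer that any earlier RRT or transplant meets the endpoint at entry. The word used is initiation, which points to a new start. A recipient with a working graft meets no component at entry, and a maintenance dialysis patient is caught mainly through the eGFR threshold.

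**Conclusion.** The point holds for the eGFR<15 component: followed as written, the plan would score patients with pre-existing stage 5 disease as progressing. The direction is toward no difference. Under an assumed prevalence of 0.5% to 2% in both groups, the crude risk ratio falls from 2.18 to between 1.95 and 1.59. This is an illustration. It rests on the plan's own event proportions, on equal prevalence in the two groups, and on every prevalent case being scored as an event. If no such patients are enrolled, nothing is lost.

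The RRT component is a wording mismatch between section 3.2 and sections 3.1 and 3.3, to be aligned. The protocol as a whole gives no ground for claiming that index dialysis will inflate the result.

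**What to change.** 1. For the renal endpoint only, limit the risk set to patients with pre-admission eGFR of at least 15 who were not on maintenance dialysis. Keep the others in for mortality.
2. Amend sections 4.3 and 8.3, which at present allow no such restriction.
3. Keep transplant recipients with working grafts whose eGFR is at least 15. They are at risk of the endpoint.
4. In section 3.2, define the RRT component as chronic RRT, in line with section 3.1. Temporary dialysis during the index AKI does not count. Dialysis that starts in the index AKI and never stops does count, identified through the dialysis-independence item in section 4.4. Without that last clause, a true renal outcome that can arise only in the AKI group would be lost.

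The restriction uses the pre-AKI baseline that section 3.1 already collects. A patient above 15 before admission and below 15 at the three-month sample therefore stays in the risk set, because that loss is new.

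The cost is protocol wording and a slightly smaller renal analysis: at the assumed 0.5% to 2%, about 3 to 11 of the 542 planned per group (542 × 0.005 = 2.7; 542 × 0.02 = 10.8). Since controls are matched within stage, the eGFR restriction should mostly remove whole pairs and leave the matching intact.
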